3.1. Objectives

Primary objective:

The primary objective is to obtain indications that a new rectal catheter can be used for TAI.

Secondary objective:

The secondary objective will include assessment of safety

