10.1. Statistical design, method and analytical procedures

Definition of analysis populations:

Intention to Treat (ITT) and Safety populations will be defined at a formal data review meeting before database lock. As a minimum, the data manager, the clinical manager and the statistician will be involved in the classification of subjects.

The ITT population (full analysis set) will be constituted by all subjects with valid informed consent who have been exposed to at least one Test product, with information on at least one endpoint or assessments used to evaluate the primary or secondary objective.

The Safety population will constitute by subjects who have given informed consent.

All evaluations of endpoint and assessments will be based upon the ITT population whereas adverse events and device deficiencies will be assessed based on the safety population. Invalid individual data points may be omitted from evaluations even though the corresponding subject is part of the ITT population. Any exclusion of data points will be documented.

Considering the data obtained it might be considered to make additional explorative analyses based on a subset of the ITT population.

Evaluation of endpoints and assessments:

All baseline measurements, endpoint and assessments will be summarized by descriptive statistics and/or listed. Endpoint and assessments will be summarized by product, if relevant.

Descriptive statistics for continuous variables are presented with N, Mean, SD (standard deviation), Median, Min and Max, where N denotes the number of subjects contributing with non-missing data. For discrete variables, descriptive statistics are presented with N and percentage, where percentage is based on the total number of subjects/observations with non-missing data.

As an exploratory analysis to support the aim of the investigation the proportion of successful irrigations will be compared for the two type of devices by a one-sided Fisher's Exact Test testing if the proportion with the investigational device is lower than with the Comparator device. The test will be performed on a 5% test level.

Other summaries and analyses can be made, if relevant.

As it is an exploratory clinical investigation no adjustment for multiple testing will be applied if statistical analyses are performed.

All statistical analyses and summaries are made with SAS version 9.4 (SAS Institute Inc., Cary, NC) /Enterprise Guide version 7.1.

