16.1. Adverse events

An adverse event is any untoward medical occurrence, unintended disease or injury, or untoward clinical signs (including abnormal laboratory findings) in subjects, whether related to the investigational medical device(s) or the comparator(s), or the procedures involved. The adverse event shall be marked with the intensity mild, moderate or severe. This could include events such as headache or dizziness.

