16.6. Reporting and timelines

16.7. Investigator's reporting responsibilities

- PI at each site must assess all (S)AEs that occur at his/her site.
- All serious adverse events and serious adverse device effects must be reported to sponsor within 24 hours of the site becoming aware of the event.
- A device deficiency that could have led to a serious adverse event but did not because suitable action
 was taken, intervention had been made or because of fortunate circumstances should be reported to
 sponsor within 24 hours of the site becoming aware of the event.
- New findings and/or updates in relation to already reported serious events should also be reported to sponsor within 24 hours of the site becoming aware of the event.
- Device deficiencies and all adverse device effects related to CE-marked Coloplast investigational product and/or comparator must be reported to sponsor within 24 hours of becoming aware of the event.

When reporting the SAE, the relationship to the test material shall be described whether the event is considered:

- Not related, the event has no temporal relationship with the use of the test material or the procedures.
- Unlikely related, the relationship with the use of the test material seems not relevant and/or the event can be reasonably explained by another cause, but additional information may be obtained.
- **Possible related**, the relationship with the use of the test material is weak but cannot be ruled out completely. Alternative causes are also possible (e.g., an underlying or concurrent illness/ clinical condition or/and an effect of another device, drug or treatment). Cases where relatedness cannot be assessed or no information has been obtained should also be classified as possible.
- **Probable related,** the relationship with the use of the test material seems relevant and/or the event cannot reasonably be explained by another cause, but additional information may be obtained.
- Definitely related/Causal relationship, the event has a temporal relationship with the test material use/application or procedures.

And the intensity of the event should be considered, as such:

- Mild, the intensity of the event is mild with no further action or intervention.
- Moderate, the intensity of the event will lead to an action or intervention to solve the event.
- Severe, the intensity of the event will lead to follow up on the action or intervention, as the effect of the action or intervention may not decrease the symptoms.

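### The intensity grades in section 16.7 rest on the action taken, Mild is circular, and an intense event that needs no action fits no grade; sections 16.1 and 16.7 need one intensity scale kept apart from management.

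*Combined protocol and SAP*

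**What the plan says.** Section 16.1 applies to all adverse events: "The adverse event shall be marked with the intensity mild, moderate or severe". It defines none of the three grades and does not refer to another section for them.

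The visible definitions are in section 16.7. A causality list comes first, introduced by "When reporting the SAE, the relationship to the test material shall be described whether the event is considered". The intensity list then continues it: "And the intensity of the event should be considered, as such". Three grades follow:

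- The lowest grade is worded in terms of itself: "Mild, the intensity of the event is mild with no further action or intervention".
- For the middle grade, the test is whether something was done about the event: "Moderate, the intensity of the event will lead to an action or intervention to solve the event".
- For the highest grade, the test is whether what was done has to be checked again: "Severe, the intensity of the event will lead to follow up on the action or intervention". The reason given is that the symptoms may not improve.

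On the role of safety, section 3.1 states: "The secondary objective will include assessment of safety". Section 5.3.4 lists adverse events and device deficiencies as the safety assessments. Section 10.1 says that "adverse events and device deficiencies will be assessed based on the safety population" and specifies no summary or test by intensity. Section 5.8 states that neither subjects nor health care professionals are blinded.

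**The concern.** Intensity and management are different things to record. Intensity describes the event as the subject experienced it. Action taken describes what staff did, which also depends on local habit, caution and familiarity with the device. When the second defines the first, the order of the grades need not follow the order of intensity.

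This matters more here than in a long treatment study. The investigation is first in human. Each device is used at one supervised hospital visit, by staff who know which catheter is in use. The plan's own examples of adverse events are headache and dizziness (section 16.1), and section 15.2 allows for discomfort and pain. Such reactions can be brief and settle without any action, and the scale has no place for them when they are intense. Staff may also have a different threshold for acting with an unfamiliar catheter than with a familiar one. That difference would then appear as a difference in graded intensity between the products.

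**Working it through.** The plan gives no figure to reproduce, and no formula applies. The check is to read the three definitions as a decision rule and run cases through them.

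**The rule, from section 16.7**

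- Mild has two conditions: (i) the intensity is mild, with no description of what that means; (ii) no further action or intervention.
- Moderate has one criterion: the intensity leads to an action or intervention.
- Severe has one criterion: the intensity leads to follow-up of that action, because it may not relieve the symptoms.

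No grade mentions symptom strength, tolerability or interference with activity.

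**Cases**

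| Event | Mild? | Moderate? | Severe? | Result |
|---|---|---|---|---|
| A. Slight, no action | Yes | No | No | Mild |
| B. Intense, settles by itself, no action | No: fails (i) | No: no action | No: no action to follow up | No grade |
| C. Trivial, treated | No: fails (ii) | Yes | No | Moderate |
| D. Trivial, treated, followed up because the treatment may not work | No: fails (ii) | Yes | Yes | Severe |

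Case B is the most intense of the four and has no valid grade. Section 16.1 still requires one of three, so the site must improvise, and Mild is what remains by elimination. Case D is trivial and takes the highest grade. Treatment alone, as in case C, gives Moderate and not Severe.

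**Scope of the scale.** There are two readings of sections 16.1 and 16.7 together.

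1. The section 16.7 scale applies to all adverse events. Cases B to D then follow. This reading is an inference, because the list continues text that opens with SAE reporting.
2. The scale applies to SAEs only. The grades that section 16.1 requires for non-serious events then have no visible definition.

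Both readings leave a defect, and the same correction resolves both.

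**What uses the grade.** The seriousness criteria (section 16.4), the 24-hour investigator reports (section 16.7), sponsor reporting (section 16.8) and suspension for unacceptable risk (section 17) do not refer to intensity. Nor does the primary endpoint (section 5.2). Section 10.4 sets no pass/fail criterion, and section 10.6 gives no statistical reason for termination.

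**Scale.** If a proportion by intensity were tabulated over the planned 20 randomized subjects, one regraded subject would move it by 1/20 = 5 percentage points. This is for orientation only. No such table is planned, and the safety population in section 10.1 is everyone who consented, so the denominator may differ from 20.

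**The case against.** The strongest case on the other side has five parts.

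**Mild still contains an intensity condition.** A reader might infer that the plan down-grades intense, self-limiting events to Mild. The text does not say so. Mild also requires that the intensity be mild, so such an event is unclassifiable. This stands: the defect is a gap, and Mild is reached only by elimination.

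**Intensity is worded as the driver.** Moderate and Severe both speak of intensity leading to action or follow-up, so it goes too far to say that the plan ignores how bad an event is. That is fair. But the plan does not say what level of intensity leads to action, so the action is all that a site can observe and apply.

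**Action is a broad word.** Under the full supervision described in section 8.2, pausing or observing a subject might count as an action, and an intense event would then be Moderate. This is possible and narrows case B. It also shows that the grade depends on what each site counts as an action.

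**No planned output uses the grade.** Section 10.1 allows data to be summarised or simply listed, and with about 20 subjects a listing could show each event. This stands and limits the harm. A listing would still carry the grade as entered.

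**Some material is not visible.** The adverse event form and the eCRF guide are not in the documents, and only section 5.3.4 of the assessments can be read. VAS is in the abbreviation list, and section 9.2 mentions equipment for an assessment tied to the secondary objective. Other measures of tolerability, or a separate field for action taken, may exist. Neither would repair the definitions in section 16.7.

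**Conclusion.** The point holds in a limited form. Section 16.1 demands a grade for every adverse event. The only visible definitions separate Moderate and Severe by action and follow-up, and they leave Mild circular. An intense event with no action has no valid grade. A trivial treated event is Moderate, and it is Severe only if the treatment also needs follow-up because it may not work. In an open-label study the grade is therefore partly a record of staff decisions.

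The consequence is limited to the descriptive safety data for the secondary objective. A reader might infer that serious events could be missed, that reports could be delayed, or that the primary comparison is affected. The documents do not support this, since none of these depends on intensity. No numerical bias can be stated, because the documents give no event rates and plan no table by intensity.

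The conclusion assumes that no other intensity definition exists in the form or guide that sites use. Applying the section 16.7 scale to non-serious events is an inference. If it is wrong, the finding becomes a missing definition for section 16.1. The change is worth making because it is cheap and safety is a stated objective.

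**What to change.** In section 16.7, with a cross-reference from section 16.1, state that one intensity scale applies to all adverse events, serious or not, and define it by symptoms and function:

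- Mild: noticed but easily tolerated.
- Moderate: interferes with usual activity.
- Severe: prevents usual activity.

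Do not tie any grade to whether the irrigation was completed. That would overlap with the primary endpoint and bring a decision by unblinded staff back into the grade.

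Record action taken and outcome as separate fields on the adverse event form, if they are not already there. The management information is then kept without setting the grade.

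The cost is a wording change in the CIP and the eCRF guide, possibly one or two form fields, and a short item in the site initiation training already planned in section 9.2. The small downside is that some events may be graded higher than under the current text. The change concerns measurement only and leaves the care of subjects as it is.

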16.8. Sponsors reporting responsibilities

It is the responsibility of sponsor to ensure that the following are reported to national regulatory authorities immediately, but no later than 7 calendar days following the date of awareness by sponsor:

- All SAEs.
- All SADEs.
- All device deficiencies that could have led to serious adverse events but did not because suitable action was taken, intervention had been made or because of fortunate circumstances.
- New findings and/or updates in relation to already reported events.

If the serious adverse event results in imminent risk of death, serious injury, or serious illness that requires prompt remedial action for other subjects, users or other persons or a new finding to such a serious adverse event, sponsor must immediately but no later than two calendar days after awareness by sponsor report the event to national regulatory authorities.

It is the responsibility of sponsor to inform all investigators in writing within 10 working days if device deficiencies, adverse events, adverse device effects, near-incidents, serious adverse events, serious adverse device effects or unanticipated serious adverse device effects lead to corrective actions (e.g., change of IFU).

17. Suspension or premature termination of the clinical investigation

Sponsor may suspend or prematurely terminate an investigation site or the entire clinical investigation for documented significant reasons.

If a suspicion of an unacceptable risk to subjects develops during the clinical investigation, sponsor will suspend the investigation while the risk is assessed. Sponsor will terminate the investigation if an unacceptable risk is confirmed. Sponsor will ensure that the premature termination will be justified in writing and will promptly inform the regulatory authorities and EC. If monitoring or auditing of the clinical investigation identifies serious or repeated deviations at one of the participating investigation sites, sponsor will suspend or terminate the particular investigational site. The sponsor or investigator will inform the regulatory authority as appropriate and notify the EC about the termination of the site.

18. Clinical Investigation Report

At completion of the investigation sponsor is responsible for writing the clinical investigation report. The report is retained on file. The report contains a critical evaluation of all data, which have been collected during the investigation. The report describes the methodology and design and a data analysis, including statistical preparation and conclusion.

Sponsor and coordinating investigator must sign the final version of the clinical investigation report or an affidavit, indicating their agreement with the contents. If no coordinating investigator is appointed, then the signatures of the principal investigator(s) should be obtained.

The clinical investigation report must be submitted to EC.

19. Publication policy

In accordance with the Declaration of Helsinki, a description of the clinical investigation will be registered in a publicly accessible database (www.clinicaltrials.gov) before the start of any recruitment activities. The content of the registration will be registered throughout the conduct of the clinical investigation, and the results will be entered at completion (i.e., within one year after last patient out) of the clinical investigation.

The results of the investigation, positive as well as negative, may be communicated by publications, abstracts, posters, or oral presentations. In all cases, the subject's identity will remain confidential. The terms of publication between sponsor and PIs and delegates are agreed in separate Sponsor Investigator Agreements.

No preliminary results from the clinical investigation will be published. Data from the investigation is considered confidential until it is published.

20. Suspension/termination of the clinical investigation

Sponsor will withdraw from sponsorship of the clinical investigation if:

- Major non-adherence to the clinical investigation plan is occurring.
- It is anticipated that the subject recruitment will not be adequate to meet the investigation objectives (at least 75% of the subjects should be entered within the recruitment time).

In case sponsor withdraws, sponsorship for the subjects already recruited into the clinical investigation will continue.

21. Bibliography

- 1. Emmanuel, A.V., et al., Consensus review of best practice of transanal irrigation in adults. Spinal Cord, 2013. 51(10): p. 732-8.
- 2. Mosiello, G., et al., Consensus Review of Best Practice of Transanal Irrigation in Children. Journal of Pediatric Gastroenterology and Nutrition, 2016.
